Study Rationale	
 • The COVID-19 pandemic has disproportionately impacted rural communities. • When compared to urban populations, individuals living in rural areas are more vaccine hesitant, have a higher prevalence of comorbid health conditions, and are at greater risk from SARS-CoV-2 variants. Thus, interventions to increase vaccine uptake in rural areas are greatly needed. • Community pharmacists are well-positioned to address vaccine hesitancy with underserved, rural populations. • Because vaccination conversations are sensitive and often politically charged, pharmacists need implementation support, including training and ongoing guidance to deliver evidence-based vaccine hesitancy counseling interventions • Implementation facilitation, in which trained facilitators coach and troubleshoot problems with professionals as they implement new practices, increases adoption of practices with fidelity. • Facilitation generally, and virtual facilitation (e.g., video coaching) in particular, has not been systematically studied in community pharmacy settings.
Study Objective(s)	
Primary
 
 • To evaluate whether virtual facilitation improves fidelity to the vaccine hesitancy counseling intervention when compared to standard implementation. 
Secondary
 
 • To evaluate whether virtual facilitation increases intervention effectiveness, defined as a higher number of vaccine hesitant individuals who receive the vaccine, when compared to standard implementation.
Test Article	
We have refined an evidence-based vaccine hesitancy counseling intervention with extensive feedback from rural pharmacists, resulting in a 5-step counseling process (ASORT):
 
 • Ask if they would like to receive a COVID vaccination • Solicit their main vaccine concern • Offer to address their concerns • Recommend the vaccine • Try again later if they refuse or are unsure
Study Design	This is an implementation science study. We will use a randomized clinical trial with an adapted stepped-wedge design and 30 rural

	pharmacies. Mixed methods will provide triangulation, expansion, and explanation of quantitative findings.
Subject Population key criteria for Inclusion and Exclusion:	
Data will be collected from rural pharmacies located in 7 southeastern states that participate in the Rural Research Alliance of Community Pharmacies (RURAL-CP).
 
Inclusion Criteria
 
 1. be a member of RURAL-CP 2. be located in a county that has an African American population of at least 25% or had at least 51% of the population vote for a Republican president in 2020. 3. stock the Covid-19 vaccine for the duration of the study 
Each pharmacy will contribute at least 1 pharmacist and up to 4 additional pharmacy staff members for the study. Pharmacy staff will be eligible if:
 
 • they are at least 18 years of age • they can read and speak English • they have been employed by the pharmacy for at least 1 month 
Exclusion Criteria
 
 • There are no exclusion criteria for pharmacy staff
Number Of Subjects	30 pharmacies and up to 150 subjects
Study Duration	
Pharmacies will participate in the study for 6-12 months.
 
Total anticipated study duration will be 2 years.

Study Phases	
 1. Screening: identifying pharmacies in the RURAL-CP network that meet the eligibility criteria 2. Enrollment by invitation: inviting select pharmacies via email, confirming eligibility of those interested, obtaining verbal informed consent 3. Standard Implementation Period: participants complete one or two 8-week period(s), which involves: completing a 30-minute online training; watching a webinar; implementing the vaccine hesitancy counseling intervention with 10 vaccine hesitant patients per 8-week period; meeting with an SP once per month to have their fidelity to the intervention evaluated 4. Virtual Facilitation Period: participants complete one or two 8-week period(s), which involves: a virtual site visit from a trained virtual facilitator; at least weekly calls with the facilitator; implementing the vaccine hesitancy counseling intervention with 10 vaccine hesitant patients per 8-week period; meeting with an SP once per month to have their fidelity to the intervention evaluated 5. Follow-up: select pharmacies will have one 8-week follow-up period, during which they will continue to implement the vaccine hesitancy counseling intervention with 10 vaccine hesitant patients 6. Qualitative Data Collection: select participants (12 total) will complete a 60-minute interview to assess feasibility and performance of the implementation approaches

Efficacy Evaluations	
Primary outcome: trained study staff will use a fidelity observation guide to rate pharmacists' vaccine hesitancy counseling during recorded counseling sessions. The fidelity measure focuses on the competence of the pharmacist (7 items) in their delivery of the vaccine hesitancy counseling intervention. Each competence item will be assessed on a scale from 0 to 2, with 0 = skill not demonstrated, 1 = skill needs development, and 2 = skill demonstrated with competence.
 
Secondary outcome: using an online survey, pharmacists will document the following on a daily basis:
 
 A) how many vaccine-hesitant individuals they provided vaccine hesitancy counseling to; B) of those individuals, how many received a COVID-19 vaccine; C) the self-reported age, race, and gender of the individual who was counseled. 
Effectiveness will be calculated as the proportion of counseled individuals who received a vaccine, or B/A. Scores will range from 0 to 1.

Statistical And Analytic Plan	
For the primary analysis of the fidelity outcome, linear mixed-effects models (LMM) will be used to compare the level of fidelity between the two implementation approaches (standard vs. virtual facilitation). We will report point estimates for the group mean difference along with a 95% confidence interval.
 
Generalized linear mixed models (GLMM) will be used for analysis of the secondary outcome of effectiveness.

DATA AND SAFETY MONITORING PLAN	
The study PIs will review interview and survey data as well as fidelity data on a quarterly basis for safety issues. In addition, the entire study team will meet monthly to discuss the study's progression and any potential safety or data concerns.

BACKGROUND AND RATIONALE

Major health crises like the COVID-19 pandemic have disproportionately impacted rural communities, which are frequently health professional shortage areas that lack health care infrastructure, including hospitals¹⁻³. As one of the most accessible health professionals in rural areas^{4,5}, community pharmacists are a notable exception to this lack of infrastructure. There are ≈68,000 community pharmacies in the U.S, many of which have convenient hours and offer free walk-in services⁶.

When compared to urban populations, individuals living in rural areas are more vaccine hesitant^{8,9} and have a higher prevalence of health conditions that increase their risk for severe COVID-19 illness and death¹². Higher vaccine hesitancy is strongly correlated with lower vaccination rates¹³, with rural counties driving lower state-level vaccination rates in the South^{14,15}, which has some of the lowest vaccination rates in the country. Unless vaccine hesitancy is addressed, low vaccination rates and a lack of vaccine mandates mean these communities remain susceptible to SARS-CoV-2 variants. Pharmacists, one of the most trusted sources of medication information¹⁶, can serve as strong allies to address vaccine hesitancy. Rural patients see their community pharmacist ~14 times per year; nearly three times more than they see a primary care provider¹⁷. Thus, pharmacists can address vaccine concerns on a monthly basis and make repeated vaccination offers.

To engage in sensitive vaccine conversations that pharmacists have referred to as “charged”, they need updated information to address patients’ evolving vaccine concerns and implementation support, including training and ongoing guidance, to deliver evidence-based vaccine hesitancy counseling interventions¹⁸. A *standard implementation approach*, which typically involves training and dissemination of implementation support tools (e.g., sample workflows, counseling “cheat sheets”), is commonly used to help health professionals implement new practices, including HPV vaccination¹⁹. Although necessary, this standard approach is usually not sufficient to promote adoption of a new and complex practice with fidelity²⁰⁻²². In recognition of this limitation, a growing body of research shows that *implementation facilitation* can increase implementation fidelity²³⁻²⁶ by having trained facilitators build trusting relationships with health professionals to monitor their implementation progress, provide feedback, and reinforce change. To date, implementation facilitation has not been systematically studied in community pharmacy settings. Moreover, little is known about the effectiveness of a *virtual facilitation approach*, whereby facilitators connect with health professionals *exclusively* via telephone and video. The need to study virtual facilitation is highly relevant given that travel to remote rural locations is resource-intensive and has been restricted due to pandemic-related safety concerns.

1 STUDY OBJECTIVES

The overall objective is to test the effects of a *standard implementation* approach and the addition of *virtual facilitation* on rural pharmacists' ability to implement COVID-19 vaccine hesitancy counseling, using an incomplete stepped wedge design²⁷. Data will be collected on the primary trial outcome of counseling fidelity (competence) and the secondary outcome of intervention effectiveness (vaccination rates). Pharmacies will implement the ASORT intervention, which was adapted from an evidence-based vaccine hesitancy intervention²⁸ with extensive qualitative input from rural pharmacists²⁹. The intervention will be updated frequently to address new vaccine concerns as they arise.

We have two specific aims.

1.1 Aim 1

Compared to the standard implementation approach, test whether adding virtual facilitation increases (a) the fidelity with which pharmacists implement the vaccine hesitancy counseling intervention and (b) the number of vaccine hesitant patients who receive the vaccine. Our primary outcome is pharmacist fidelity to the vaccine hesitancy counseling intervention and our secondary outcome is intervention effectiveness (i.e., the number of vaccine hesitant individuals who receive a vaccine). We hypothesize that:

H_1 : Virtual facilitation will improve fidelity to the vaccine hesitancy counseling intervention when compared to standard implementation.

H_2 : Virtual facilitation will increase intervention effectiveness, defined as a higher number of vaccine hesitant individuals who receive the vaccine, when compared to standard implementation.

1.2 Aim 2

Conduct a cost assessment and explore potential sustainability of the implementation approaches. We will conduct a time-driven, activity-based cost analysis and a budget analysis of the standard implementation and virtual facilitation approaches. Additionally, a payer advisory board will review these data and advise on how to make virtual facilitation sustainable through reimbursement models. We do not have a hypothesis associated with this aim.

2 INVESTIGATIONAL PLAN

2.1 Study Design

This is an implementation science study. We will use a randomized clinical trial with an adapted stepped-wedge design and 30 rural pharmacies to determine the effectiveness and incremental cost-effectiveness of a standard implementation approach compared to the addition of virtual facilitation by a trained facilitator in support of the delivery of a COVID-19 vaccine hesitancy counseling intervention. Mixed methods will provide triangulation, expansion, and explanation of quantitative findings.

In the incomplete stepped wedge cluster randomized design, each pharmacy will begin in the standard implementation approach condition for one or two 8-week periods and then "crossover" to the virtual facilitation condition for one or two 8-week periods. Length of time in each condition depends on the "step" to which pharmacies are randomly assigned. Figure 1 depicts the "stairstep" study design and

pharmacy assignment. For blocks 1–4, we will continue to collect data during one 8-week follow-up period to evaluate the potential impact of the virtual facilitation approach on sustained intervention fidelity and effectiveness once virtual facilitation has been stopped.

2.2 Allocation to Treatment Groups

In this stepped-wedge trial, pharmacies will be randomized in blocks at the time they begin the initial intervention condition (standard implementation). We will create 6 blocks of pharmacies, with 5 pharmacies randomized to each block by the trial statistician. To ensure balance, the block randomization will be stratified by two measures of pharmacy size—the number of patients and number of pharmacists.

2.3 Number of Subjects and Study Duration

The stepped-wedge trial includes 30 pharmacies and up to 150 subjects. Subjects will include 30 pharmacists (1 from each pharmacy) and up to 120 pharmacy staff (up to 4 staff from each pharmacy), such as pharmacy technicians and cashiers. Pharmacies will participate in the study for 6-12 months, depending on the block to which they are randomly assigned. Total anticipated study duration will be 2 years, with 15 pharmacies participating in year 1 and 15 participating in year 2. The study follows the distribution of COVID-19 vaccines in the USA, which follows the Northern Hemisphere’s “flu season”—approximately August–February each year. We expect that the first COVID-19 vaccination season in the fall of 2023 will be delayed due to vaccine availability and will begin in October and run through March 2024. In 2024, we expect that availability issues will not occur and the vaccine will be available during the standard flu season from August–February. All pharmacies begin the study in the fall. Block 1 and blocks 4–6 will participate for 6 months (Oct–Mar and Aug–Jan, respectively). Blocks 2 and 3 begin in Oct 2023 and participate for 6 months alongside Block 1, but then have an 8-week follow-up period Aug–Sep 2024 (Figure 1).

2.4 Study Population

All data will be collected from rural pharmacies that participate in the Rural Research Alliance of Community Pharmacies (RURAL-CP), which was established by this trial’s multiple principal investigators [name] and [name] in 2020. RURAL-CP is the first practice-based research network for rural community pharmacies and aims to reduce rural health disparities by supporting high-quality implementation research with community pharmacies. Thirty pharmacies will be recruited from a total of 127 RURAL-CP pharmacies located in seven states throughout the Southeast. For a pharmacy to be eligible for the trial, it must: be a member of RURAL-CP; be located in a county that has an African American population of at least 25% or had at least 51% of the population vote for a Republican president in 2020. The reason for this criterion is that these populations are more vaccine hesitant; and stock the Covid-19 vaccine for the duration of the study. Each pharmacy will contribute at least 1 pharmacist and up to 4 additional pharmacy staff members for the study, including pharmacy technicians and cashiers. Pharmacy staff will be eligible if: they are at least 18 years of age; they can read and speak English; and they have been employed by the pharmacy for at least 1 month. There are no exclusion criteria for pharmacy staff.

3 STUDY PROCEDURES

3.1 Recruitment

Study staff have identified pharmacies in the RURAL-CP network that meet the eligibility criteria. The program manager for RURAL-CP will inform all eligible member pharmacies about the proposed study via email and ask interested pharmacies to respond stating their interest. Subsequent discussions will explain the purpose of the study and study procedures. Pharmacies interested in participating will identify potential pharmacy staff respondents and provide their contact information to the PIs. These potential respondents will be contacted by study staff to ask them if they would like to participate in the study. A consent script will be created by the research team for recruitment that will include a description of the study and what will be expected of participants. Verbal consent will be obtained from all subjects.

3.2 Standard Implementation Period

After pharmacy participants are enrolled, they will then complete one or two 8-week "standard implementation" period(s), depending on the step to which they are randomly assigned. At the beginning of this period, they will be asked to complete a 30-minute online training about COVID-19 vaccine hesitancy counseling and watch a live or pre-recorded webinar (their choice) that provides up-to-date information about COVID-19 vaccinations and boosters. After completion of the training and webinar, participants will be asked to implement the vaccine hesitancy counseling intervention with 10 vaccine hesitant patients per 8-week period. Pharmacists will use Qualtrics or a paper survey to document the extent to which the intervention results in customers getting vaccinated. They will specifically document the number of customers they offered the intervention to, the number who refused, and the number who agreed to be vaccinated. No identifiable customer-level data will be provided by the pharmacies.

Additionally, during the standard implementation period(s), trained study staff will observe and rate counseling fidelity two times per month for each participating pharmacy. We will use a fidelity rating scale to assess fidelity of delivery of the intervention during 4-8 total observed intervention sessions per pharmacy (4 per 8-week period). Since pharmacists have reported difficulties getting patients to agree to be recorded, affecting data collection, we will use standardized patients (SPs) in lieu of real patient conversations. Two SPs will have a total of 8 standardized scripts, each expressing different concerns about the Covid vaccine. The project manager will schedule a 20-minute block with an SP and participating pharmacist and send a Zoom link. Pharmacists will be randomized to script and order of the presentation of two SP scenarios. On the Zoom call, SPs will enact two of their cases, to which the pharmacist will ideally respond with the ASORT intervention. The encounter will be recorded using the secure Express Dictate mobile or desktop app and later rated for counseling fidelity. SPs will meet with each pharmacist one time per month, portraying different personas each time.

To increase the likelihood that each participating pharmacy submits the requested study data, a fax will be sent to each participating pharmacy that is missing data after the first month of standard implementation to remind them of what is needed. This fax may be sent every 2 weeks as needed to acquire missing study data, with a follow-up phone call a week after the fax to non-responders.

At the end of the standard implementation period(s), participating pharmacy staff (up to 5 per pharmacy) will complete Qualtrics surveys to assess implementation outcomes (feasibility, acceptability, appropriateness).

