3.3 Virtual Facilitation Period

After the implementation outcome surveys have been completed, pharmacies will "crossover" to the virtual facilitation period(s). This period will begin with a virtual site visit from a trained virtual facilitator and be followed by at least weekly calls with a local champion (a participating pharmacist) and at least bi-weekly calls with each participating pharmacist to provide feedback on intervention fidelity (from observations of interventions delivered). The virtual site visit over Zoom will establish the personnel and workflows at each pharmacy and allow the facilitator to establish rapport. Weekly Zoom calls will allow the virtual facilitator to work with a site champion to review overall implementation challenges associated with approaching patients, delivering the intervention, and documenting results. Lastly, either the facilitator or the local champion can request and schedule a Zoom call to go over any pressing implementation issue in need of rapid attention (e.g., technical difficulties with the website).

During each 8-week virtual facilitation period (one or two periods, depending on the step to which pharmacies are randomly assigned), pharmacists will again be asked to implement the intervention with 10 vaccine hesitant patients. Like during the standard implementation period, pharmacists will use Qualtrics or a paper survey to document the extent to which the intervention results in customers getting vaccinated. Similarly, fidelity observations (4-8 total per pharmacy) will be collected using the same processes described in Section 3.2. Additionally, at the end of virtual facilitation period(s) participating pharmacy staff (up to 5 per pharmacy) will again be asked to complete Qualtrics surveys to assess implementation outcomes (feasibility, acceptability, appropriateness).

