5.1 Primary Outcome

The primary outcome of fidelity is captured at the pharmacy level. For our primary analysis of the fidelity outcome, we will use linear mixed-effects models (LMM) to compare the level of fidelity between the two implementation approaches (standard approach vs. virtual facilitation). We will report point estimates for the group mean difference along with a 95% confidence interval. The model-building approach will follow four analyses steps: 1) an unadjusted before/after of the effect of the virtual facilitation approach (ignoring period/time effect); 2) the time period (i.e., steps/blocks) to examine if any potential intervention effect relates only to the intervention or also to an independent effect of calendar time; 3) an adjustment for potential pharmacy-level confounders, such as size and learning climate; and 4) the interaction between period and intervention effect.

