Sustainment	Continued measurement of fidelity, effectiveness, and uptake during the "follow-up" periods	See above entries for fidelity, effectiveness, and uptake	
Cost	Costs associated with deployment of each implementation approach.	Log of time and activities completed monthly by facilitator	

† qualitative data will be collected after the end of the virtual facilitation period with 1 high performing and 1 low performing pharmacies per block

Table 2: Selected content from the 5-step vaccine hesitancy counseling process (ASORT)

Step	Recommendations & Example Verbiage
Ask if they would like to receive a COVID vaccination	
 People are more open to talking about the COVID-19 vaccine if you ask while you're doing other activities, like giving a flu shot or engaging in medication therapy management. "While I'm giving your flu shot, I just thought I'd ask if you've gotten your COVID vaccine yet." Offer praise to people who are up-to-date on their vaccination
Solicit their main vaccine concern	
 People often have multiple concerns about the vaccine, but one concern will likely loom larger than the others, so this is the concern you'll want to focus on first. "Can you tell me more about that?"
Offer to address their concerns	
 People have different levels of readiness to discuss the vaccine, so it's important to ask for permission to share more information about their concerns. Start by validating their concerns so they know that you're not judging them. "I know several other people who have had that same concern and I've shared some information with them that they've found useful. I'd be happy to share that same information with you if you want." Some people won't be ready for more information and that's okay. Just let them know that you understand. "Ok. No problem. Know that I'm here if you do ever want to talk." Address their concerns For individuals who aren't ready, skip to the last step.

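### Eight standardized-patient scripts cannot cover the 12 rated encounters in blocks 2, 3, 5 and 6: at least 80 of 320 ratings repeat a script, which can bias the time-ignoring model and the sustainment contrast.

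*Combined protocol and SAP*

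**What the plan says.** Section 3.2 sets the size of the script bank: "Two SPs will have a total of 8 standardized scripts, each expressing different concerns about the Covid vaccine". On each call, "On the Zoom call, SPs will enact two of their cases, to which the pharmacist will ideally respond with the ASORT intervention". The frequency is also fixed: "SPs will meet with each pharmacist one time per month, portraying different personas each time". The resulting count for the standard condition is given as "4-8 total observed intervention sessions per pharmacy (4 per 8-week period"). Section 3.3 carries the method over to facilitation: "fidelity observations (4-8 total per pharmacy) will be collected using the same processes described in Section 3.2". No second script set is described. Scripts and their order are randomized, but nothing says whether a script may return in a later month or which of the two standardized patients a pharmacist meets.

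Section 5.1 lists four model steps for fidelity. The first is "an unadjusted before/after of the effect of the virtual facilitation approach (ignoring period/time effect"). The second adds time, glossed as steps/blocks. None is named as the primary estimate.

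On follow-up, Table 1 (Appendix) defines sustainment as "Continued measurement of fidelity, effectiveness, and uptake during the" follow-up periods, and Sections 2.1 and 4.3 agree. Section 3.4, which describes follow-up procedures, lists only vaccination documentation.

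**The concern.** Each script carries its own vaccine concern, and one of the seven scored competence items (Section 4.1) is whether the pharmacist answers concerns with evidence-based responses. A pharmacist who has met a script before can prepare for it. Because every pharmacy moves from standard to facilitation, repeats tend to fall late, and so in facilitation. A gain from having seen the script could then be read as a benefit of facilitation or, if follow-up is rated, as sustained fidelity.

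**Working it through.** **Inputs.** 8 scripts, 2 cases per call and 1 call per month (Section 3.2); the same process in facilitation (Section 3.3); 6 blocks of 5 pharmacies (Section 2.2); one pharmacist per pharmacy (Section 2.3); sequences from Figure 1; difference 0.53, SD 1, ICC 0.6, two-sided alpha 0.05 (Section 5.3). Assumptions not in the documents: an additive rehearsal gain of g SD, the same in all blocks, and a cluster autocorrelation (CAC) of 0.8 to 1. CAC 1 is a simple random pharmacy intercept.

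**The plan's own figures.** Each cell holds 5 pharmacies × 4 encounters = 20. Figure 1 has 8 standard and 8 facilitation cells: 160 + 160 = 320, as stated. Generalized least squares (GLS) with categorical period and CAC 1 gives SE 0.152. Power is Φ(0.53/0.152 − 1.96) = 93.6%, consistent with the stated value of over 90%.

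**Shortage.** Blocks 1 and 4: 2 periods × 4 = 8 encounters, just covered. Blocks 2, 3, 5 and 6: 3 × 4 = 12, so 12 − 8 = 4 forced repeats per pharmacist. Over 20 pharmacists that is at least 80 repeats. If follow-up is rated, blocks 1 and 4 reach 12 encounters and blocks 2 and 3 reach 16.

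**Where repeats fall.** This depends on the unstated rule:

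| Allocation rule | Standard (of 160) | Facilitation (of 160) |
|---|---|---|
| No reuse until all 8 are used | 0 | 80 |
| Avoid only the previous month's scripts | about 18 | about 96 |
| Independent random pair each month | about 35 | about 98 |
| One standardized patient throughout, 4 scripts | 40 | 160 |

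**Bias.** Let r = 1 for a repeat encounter under the no-reuse rule, which is the third period of each sequence and any follow-up. The bias is g times the facilitation element of (X′V⁻¹X)⁻¹X′V⁻¹r.

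| Model | Bias on facilitation |
|---|---|
| Step 1, time ignored | 0.54g |
| Block only | 0.55g |
| Linear time | 0.13g at ICC 0.6, up to 0.43g at ICC 0.05 |
| Categorical calendar period, standard and facilitation cells | 0 |
| Categorical period, follow-up fitted jointly with its own term | 0.18g (CAC 1) to 0.25g (CAC 0.8) |

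In the last model the bias on the follow-up (sustainment) term is 0.37g to 0.52g.

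Hand check of the block-only value, using within-pharmacy sums. Exposure variation is 1/2 for S-F, 2/3 for S-S-F and 2/3 for S-F-F, total 11/6. Its cross-product with r is 0, 2/3 and 1/3, total 1. The ratio is 6/11 = 0.55.

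**False-positive rate under no facilitation effect at g = 0.2.** The rate is Φ(δ − 1.96) + Φ(−δ − 1.96), with δ = bias/SE.
- Step 1, CAC 1: δ = 0.109/0.074 = 1.47, rate 31%.
- Step 1, CAC 0.9: δ = 0.108/0.093 = 1.16, rate 21%.
- Step 1, CAC 0.8: δ = 0.108/0.109 = 0.99, rate 17%.
- Categorical period with follow-up pooled: δ = 0.036/0.130 = 0.27 at CAC 1 and 0.051/0.178 = 0.29 at CAC 0.8, rate about 5.9% in both.

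At g = 0.2 the step 1 bias is 0.11 SD, about 20% of the planned 0.53.

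**Why categorical period removes the bias.** All blocks in a year start together, so the number of earlier calls is the same for every pharmacy within a period. The third period of each year has no standard cell, so the facilitation effect rests on the second period, where no repeat is forced. Follow-up ratings break this: in Aug–Sep 2024 blocks 2 and 3 would contribute only repeats, while blocks 4–6 meet the scripts for the first time.

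**The case against.** The strongest defence is that the model that uses the stepped-wedge randomization is unaffected. With categorical period on the 320 planned assessments the bias is exactly zero, and 320 counts standard and facilitation cells only, so follow-up is outside the planned comparison. That stands. A reader might infer that rehearsal is confounded with facilitation whatever the analysis; the documents do not support that.

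A reader might also take the 80 versus 0 split as fact. The shortage forces the number of repeats, not their place. The phrase "portraying different personas each time" suggests no reuse, but a persona need not be a script and the randomization sentence sets no such rule. The direction is the same under every rule tested; the split is not.

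Third, step 1 is labelled unadjusted, and any practice or calendar trend would bias it however many scripts exist. That is true. But Section 5.1 does not say which step carries the conclusion, and its description of time does not clearly mean categorical calendar period, so the protection is available without being specified.

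Finally, g may be small. Six of the seven competence items are general communication skills, only 2 of 14 points depend directly on the concern, and pharmacists already have example wording for over 25 concerns. This is fair, and it is why the size is given per unit of g.

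**Conclusion.** The point holds in a limited form. The shortage is arithmetic: at least 80 of 320 encounters must repeat a script, and the plan has no rule for which. The consequence depends on the analysis. Under no reuse until the bank is spent, the time-ignoring model carries 0.54g, with a false-positive rate of 17–31% at g = 0.2. The categorical-period comparison on the planned assessments carries none. Pooling follow-up ratings costs the facilitation estimate little (about 5.9% against 5% at g = 0.2); the sustainment contrast takes the larger bias of 0.37–0.52g. These figures rest on an additive gain of assumed size and on CAC 0.8 to 1. Whether fidelity is rated in follow-up at all must be reconciled between Sections 2.1, 4.3 and Table 1 on one side and Section 3.4 on the other. The flaw is worth removing because it is cheap to remove; it does not invalidate the trial.

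**What to change.** 1. Extend the script bank to at least 12, or 16 if fidelity is rated in follow-up, drawing on the existing list of over 25 concerns (Section 6.1).
2. Randomize scripts without replacement within pharmacist, and state this in Section 3.2.
3. Record script identity for every encounter and include script as an effect in the linear mixed model.
4. In Section 5.1, base the facilitation conclusion on the model with categorical calendar period, not on step 1.

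A first-versus-repeat covariate is not an adequate substitute in the categorical-period model without follow-up ratings. Under the no-reuse rule, repeat exposure is the third period of each year, so it is collinear with the period effects and cannot be estimated.

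The cost is writing and rehearsing 4 to 8 further scripts. No extra encounters or raters are needed. More scripts do not cure other practice or calendar trends in step 1, which is why item 4 is needed as well.
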